9.5 RULES FOR AMENDING PROTOCOL

All amendments must be documented, dated and signed by all signatories (or their successors) of the original protocol. Protocol amendments only for logistical or administrative changes may be implemented immediately; however, both the IEC/IRB and USFDA will be notified immediately.

9.6 FINANCIAL DISCLOSURE

Investigators are required to provide financial disclosure information to the Sponsor to permit the Sponsor to fulfil its obligations under 21 CFR §54. In addition, Investigators must commit to promptly updating this information if any relevant changes occur during the study and for a period of 1 year after the completion of the study. Details of insurance coverage will be covered in separate document/CTA/agreement.

9.7 DISCONTINUATION OF THE TRIAL BY THE SPONSOR

The Sponsor reserves the right to discontinue this trial at any time for failure to meet expected enrolment goals, for safety or any other administrative reasons. The Investigator will be reimbursed for reasonable expenses incurred if it is necessary to terminate the trial as per the agreement.

Approved by:
[name]

Protocol No. SARO.16.004
Version No.: 6.0

**Zydus Discovery
DMCC**

CLINICAL TRIAL PROTOCOL

Saroglitazar Magnesium – Phase II

SARO.16.004

CONFIDENTIAL

PAGE 74 OF 82

9.9 FINAL REPORT AND PUBLICATION POLICY

A report will be prepared under the responsibility of Investigators and according to the standards of the Sponsor. It will include the tabulated raw data and the biostatistical report on the data.

Zydus Discovery DMCC (ZYDUS) is as much as possible dedicated to support process of free exchange of relevant scientific information. Any publication of the results of this trial must be consistent with the ZYDUS publication policy. The rights of the Investigator and of the Sponsor with regard to publication of the results of this trial are described in the Investigator agreement.

9.10 ARCHIVING

Subject's files, identification codes and other source data (including original reports of test results, dispensing logs, records of informed consent), IEC/IRB approval letter, correspondence and other documents pertaining to the conduct of the trial will be kept as per the applicable regulatory requirements. According to ICH guidelines, essential documents should be retained for a minimum of 2 years after the last approval of a marketing application in an ICH region and until there are no pending or contemplated marketing applications in an ICH region or at least 2 years have elapsed since the formal

Approved by:
[name]

Protocol No. SARO.16.004
Version No.: 6.0

**Zydus Discovery
DMCC**

CLINICAL TRIAL PROTOCOL

Saroglitazar Magnesium – Phase II

SARO.16.004

CONFIDENTIAL

PAGE 75 OF 82

discontinuation of clinical development of the investigational product. However, these documents should be retained for a longer period if required by the applicable legal requirements. No document pertinent to the trial shall be destroyed without prior written agreement between the Sponsor and the Investigator.

Approved by:
[name]

Protocol No. SARO.16.004
Version No.: 6.0

11 APPENDICES

1. PBC-40 Questionnaire

2. Normal Reference Range of Laboratory Parameters

Approved by:
[name]

Protocol No. SARO.16.004
Version No.: 6.0

Zydus dedicated to life Zydus Discovery DMCC	CLINICAL TRIAL PROTOCOL Saroglitzaz Magnesium – Phase II SARO.16.004	CONFIDENTIAL PAGE 80 OF 82
--	--	---

0. REVISION HISTORY

This is the first revision (Version 2.0) to the Statistical Analysis Plan dated April 03, 2018. This revision was conducted to include an interim analysis that will be conducted when approximately 24th active randomized subject completes the study as per the protocol amendment version 6.0, dated August 21, 2019.

1. INTRODUCTION

The purpose of this document is to provide a description of the statistical methods and procedures to be implemented for the analysis of data from SARO.16.004 study. This document is based on protocol version 6.0. The statistical planning and conduct of analysis of the data from this study will follow the principles defined in relevant International Conference of Harmonization (ICH)-E9 guidelines. If more appropriate analytic procedures become available during the study, the statistical analysis plan (SAP) may be revised. Any revisions to the SAP (both alternative and additional methods) will be made prior to database lock and reasons for such revisions will be described in the final Clinical Study Report.

2. STUDY OBJECTIVES AND DESIGN

2.1 Study Objectives

Primary Objective

To investigate the effect of a 16-week treatment regimen of Saroglitzazar magnesium 2 mg and 4 mg on ALP levels in patients with Primary Biliary Cholangitis (PBC).

Secondary Objectives

- To compare the effect of Saroglitzazar magnesium (2 mg and 4 mg) and placebo on below mentioned parameters following a 16-week treatment in patients diagnosed with PBC:
 - Alkaline Phosphatase
 - Lipids profile: TG, TC, HDL, LDL, and VLDL
 - Liver biochemistries: GGT, ALT, AST, bilirubin and albumin.
 - Serum total bile acids
 - 7 α -hydroxy-4-cholesten-3-one (C4)
 - Fibroblast growth factor 19 (FGF19)

Document Title:	Statistical Analysis Plan		
Version Number:	2.0	Date:	11 Nov 2019
Protocol Number:	SARO.16.004	Sponsor Name:	Zydus Discovery DMCC

- Proportion of patients with ALP improvement.
- Quality of life (QoL) by using PBC-40.
- Safety and tolerability of Saroglitazar magnesium 2 mg and 4 mg
- Pharmacokinetics of Saroglitazar

[figure not shown]
2.2 Study Description

2.2.1 Study design

This is a Phase 2 prospective, multicenter, randomized, double-blind, placebo-controlled study in subjects diagnosed with PBC meeting pre-specified inclusion/exclusion criteria. Male and female subjects aged 18 to 75 years of old will be enrolled in this study. Approximately 36 subjects who meet the inclusion and exclusion criteria will be randomized in a 1:1:1 ratio to have 12 subjects in each arm i.e., Saroglitazar magnesium 2 mg, Saroglitazar 4mg and placebo respectively.

[figure not shown]
A total of 18 subjects, six subjects in each treatment group are planned for pharmacokinetic assessment. Additional subjects may be enrolled into the study to ensure the pharmacokinetic assessment is performed on at least 6 completed subjects in each treatment group.

This study will be conducted over a period of up to 26 weeks and will include a 6-week screening phase, a 16-week double-blind treatment phase and a safety follow-up visit, 4 weeks after the treatment phase. The study plan is provided below.

Document Title:	Statistical Analysis Plan		
Version Number:	2.0	Date:	11 Nov 2019
Protocol Number:	SARO.16.004	Sponsor Name:	Zydus Discovery DMCC

2.2.2 Study plan

Document Title:	Statistical Analysis Plan		
Version Number:	2.0	Date:	11 Nov 2019
Protocol Number:	SARO.16.004	Sponsor Name:	Zydus Discovery DMCC

Document Title:	Statistical Analysis Plan		
Version Number:	2.0	Date:	11 Nov 2019
Protocol Number:	SARO.16.004	Sponsor Name:	Zydus Discovery DMCC

Document Title:	Statistical Analysis Plan		
Version Number:	2.0	Date:	11 Nov 2019
Protocol Number:	SARO.16.004	Sponsor Name:	Zydus Discovery DMCC

2.3 Randomization

An independent statistician will generate the randomization schedule(s) for study treatment assignment. Eligible subjects will be randomized in a 1:1:1 ratio to receive Saroglitzaz magnesium 2 mg, Saroglitzaz magnesium 4 mg or placebo, respectively. Block randomization will be performed. The randomization schedule will be generated to ensure the treatment balance by using SAS® software (Version: 9.4 or higher; SAS Institute Inc., USA).

2.4 Blinding and Unblinding

This study is double-blinded. The subjects, investigators and all members of the Clinical Study Team will be blinded to treatment assignments while the study is in progress except the personal involved in the interim analysis. Once the 24th active randomized subject has completed the study (Week 20 visit assessment), an interim analysis will be performed with an unmasking of specified Zydus individuals (Study Director and Lead PI) who are not involved in the conduct of the trial. Treatment masking of individual subjects will remain intact for all subjects, Investigators, and staff from the Sponsor who have contact with subjects or Investigators or those who are involved in the direct conduct of the study until all planned randomized subjects complete the study and final database lock has occurred.

The formulation of Saroglitzaz magnesium (2 mg and 4 mg) and placebo IPs will be similar in appearance to make any difference in treatment unobvious to the subjects and to maintain adequate blinding of evaluators.

In an emergency, when knowledge of the subject's treatment assignment is essential for the clinical management or welfare of the subject, the investigator should make every effort to first contact the Sponsor/ designee. Prior to unblinding the subject's treatment assignment, the investigator should assess the relationship of an adverse event to the administration of the study drug (Yes or No). If the blind is broken for any reason, the investigator must record the date and reason for breaking the blind on the appropriate electronic case report form and source documents.

2.5 Interim Analysis

An interim analysis will be conducted when approximately 24th active randomized subject has completed the study, that is Week 20 visit assessment. The purpose of this interim analysis is to assess the further development of Saroglitzaz Magnesium in PBC patients and to choose the optimal dose for planning the phase III study. This analysis will evaluate the efficacy based

Document Title:	Statistical Analysis Plan		
Version Number:	2.0	Date:	11 Nov 2019
Protocol Number:	SARO.16.004	Sponsor Name:	Zydus Discovery DMCC

on liver biochemistries and lipid profiles and will summarize patient demographics and adverse events. No subject level data listing will be generated.

To ensure the integrity of the study data and compliance with the protocol, unmasking of the study is restricted to selected individuals at Zydus as specified in section 2.4. None of the individuals performing the analyses or the individuals informed of the outcome are part of the study team and from the specific time point of unmasking, none of them will be involved in the study conduct related decision making.

3. ANALYSIS POPULATIONS

Subject evaluability and their impact on analysis populations will be determined prior to breaking the blind treatment assignment code and locking the database.

3.1 Efficacy Analysis Populations

The modified intent-to-treat (MITT) population includes all randomized subjects who received at least one dose of study drug and have at least one post-randomized efficacy assessment. The MITT population will serve as the primary population for all efficacy analyses. Last observation carried forward (LOCF) method will be used as an imputation method for the efficacy variables for MITT analysis.

The supportive analysis of the primary and secondary efficacy endpoints will be conducted using the per-protocol population (PP). The PP population includes all randomized subjects who meet all the inclusions and exclusion criteria, completed the treatment phase and have not deviated from or violated the protocol in such a way that could affect the primary efficacy outcome.

The number of subjects excluded from MITT and PP populations and a listing of excluded subjects from each analysis population with reason for exclusion will be presented. Any inconsistencies in key study results between MITT and PP populations will be examined and discussed in the study report. All efficacy analysis will be conducted according to randomized treatment assignment.

3.2 Safety Analysis Population

The safety population includes the subjects who are randomized and received at least single dose of study medication. For safety analyses, subjects will be analyzed according to the actual treatment received.

Document Title:	Statistical Analysis Plan		
Version Number:	2.0	Date:	11 Nov 2019
Protocol Number:	SARO.16.004	Sponsor Name:	Zydus Discovery DMCC

3.3 Pharmacokinetic Analysis Population

The pharmacokinetic analysis population includes all randomized subjects who have at least one plasma sample collected following exposure to the study drug and have no known specimen collection or analytical deviations which would affect the integrity of the data.

4. SAMPLE SIZE AND POWER CALCULATIONS

This proof of concept study will include a total 36 subjects. No formal sample estimation was done. Subject will be enrolled in 1:1:1 ratio to have 12 subjects in each arm i.e., Saroglitzazar magnesium 2 mg, Saroglitzazar magnesium 4 mg and placebo. Six patients in each group are planned for pharmacokinetic assessment therefore a total of 18 patients will be included. Additional patients may be enrolled into the study to ensure the pharmacokinetic assessment is performed on at least 6 completed patients in each treatment arm. Additional patients will be enrolled if the dropout rate is more than 20%.

5. SUBJECT CHARACTERISTICS AND STUDY CONDUCT SUMMARIES

Disposition of Subjects

Subject disposition table will be based on all enrolled subjects who are consented to participate in the study. The following summaries will be included in the disposition table: total number of subjects screened in the study, number of subjects who failed screening, number of subjects who were randomized, number of subjects received treatment, number of subjects who completed the study, and number and percentage of subjects who discontinued from the study with reason for discontinuation. Percentages will be based on the number of patients who are randomized. This tabulation will be done overall as well as by treatment. In addition, the number of subjects included in each analysis population (MITT, PP, Safety, PK) will be presented separately.

Demographic and Baseline Characteristics

Demographic and baseline characteristics will be summarized based on the MITT, PP and Safety populations.

Descriptive summaries will be provided for the demographic and baseline characteristics. Demographic characteristics such as age, gender, race, ethnicity, AST, ALT, ALP, total bilirubin (TB), INR, ECG, vitals, height and weight will be summarized and tabulated by treatment for all the analysis populations. All the continuous variables (i.e., age, height etc.)

Document Title:	Statistical Analysis Plan		
Version Number:	2.0	Date:	11 Nov 2019
Protocol Number:	SARO.16.004	Sponsor Name:	Zydus Discovery DMCC

will be summarized by n, mean, standard deviation, minimum, median and maximum values. All the categorical variables (i.e., gender) will be summarized as counts and percentages.

Chi-square test will be used to compare the differences in categorical variables between the treatment groups and the one-way analysis variance will be used for the continuous variables.

The average of two assessments (Visit 1 and Visit 2) of liver biochemistries and INR will be considered as baseline values. In case of missing value at any one of the visits, the available value will be considered as baseline.

Medical history, previous and concomitant therapies

Previous therapies are the therapies/medications with stop date prior to the Baseline visit. Any therapy/medication usage at or post Baseline visit is considered concomitant therapy.

A list of complete medical history, including current and past diseases and their respective treatments will be provided by investigational site and subject number and treatment group.

All the concomitant medications will be listed by investigational site and subject number.

All the concomitant medications taken during the study period will be summarized by treatment group.

A summary will be provided for the number and percent of subjects who had previous therapies/medications and a separate summary of subjects who had concomitant therapy/medications. The summary of medical/disease history will be tabulated using frequency and percentages.

All medications administered during the study will be listed and coded using the World Health Organization (WHO) Drug Reference List (version DDEBSEP16). A listing of all prior and concomitant medications including the reported term, preferred term, Anatomical Therapeutic Chemical (ATC) class, start dates, stop dates and other relevant data will be provided. Concomitant medications include all medications taken on or after the date of the first dose of study drug. Prior medications include all medications taken before the date of the first dose of study drug and discontinued before the first dose of study drug.

Document Title:	Statistical Analysis Plan		
Version Number:	2.0	Date:	11 Nov 2019
Protocol Number:	SARO.16.004	Sponsor Name:	Zydus Discovery DMCC

6. EFFICACY ANALYSIS STRATEGY

6.1 General Considerations

Categorical variables will be summarized with the frequency and percentage of patients in each category. Continuous variables will be summarized descriptively with the number of subjects, mean, standard deviation, minimum, median and maximum values. Change from baseline will be summarized similarly, but also with standard error. The change from baseline will be calculated as follows:

Change from baseline = Post baseline value – Baseline value

Percent Change = (Post baseline value – Baseline value) / Baseline value * 100.

Decimal Precision

Unless otherwise noted, means, medians, standard deviations, minimums and maximums will be presented to two decimal places, percentages and confidence intervals will be presented to one decimal places; and p-values will be presented to four decimal places.

Missing Date Procedures

Adverse events with completely missing dates will be considered treatment-emergent.

Medications with completely missing end dates will be considered concomitant. Adverse events and medications with partially missing start or end dates will be considered treatment-emergent and concomitant respectively unless the non-missing portion of the dates definitively proves otherwise.

For example, if a subject starts treatment on 20FEB2016, then adverse events with onset dates of FEB2016, 2016, or 05DEC would all be considered treatment-emergent, while onsets dates of 2015 or JAN2016 would not be considered treatment-emergent. Medications starting or ending in FEB2016 or 2016 would be considered concomitant, medications ending in JAN2016 or 2015 would not.

6.2 Efficacy Endpoints

Primary Endpoint:

The primary efficacy endpoint is the change from baseline in alkaline phosphatase (ALP) at Week 16 in Saroglitzazar magnesium (2 mg and 4 mg) treatment.

Document Title:	Statistical Analysis Plan		
Version Number:	2.0	Date:	11 Nov 2019
Protocol Number:	SARO.16.004	Sponsor Name:	Zydus Discovery DMCC

Secondary Endpoints:

The following secondary efficacy endpoints will be evaluated in Saroglitzazar magnesium (2 mg and 4 mg) treatment as compared to placebo:

- Change from baseline in ALP at Week 4, Week 8, and Week 12 and Week 16.
- Change from baseline in lipid profile (TG, TC, HDL, LDL and VLDL) at Week 4, Week 8, Week 12 and Week 16.
- Change from baseline in liver biochemistries (GGT, ALT, AST, bilirubin and albumin) at Week 4, Week 8, Week 12 and Week 16.
- Change from baseline in serum total bile acids at Week 4, Week 8, Week 12 and Week 16.
- Change from baseline in 7 α -hydroxy-4-cholesten-3-one (C4) at Week 16
- Change from baseline in fibroblast growth factor 19 (FGF 19) at Week 16.
- Proportion of subjects with ALP improvement of 15%, 20%, 30%, 40% and normalization at Week 8 and Week 16.
- Change from baseline in QoL at Week 16 by using PBC-40.
- Safety and tolerability of Saroglitzazar magnesium 2 mg and 4 mg.
- Pharmacokinetics of Saroglitzazar.

6.3 Efficacy Hypotheses

The statistical hypothesis to test the primary efficacy endpoint, change in ALP from baseline to Week 16 for Saroglitzazar magnesium 2 mg and Saroglitzazar magnesium 4 mg are:

$$H_0: \mu_s \leq 0$$

$$H_1: \mu_s > 0$$

Where μ_s = change from baseline in ALP levels for Saroglitzazar magnesium 2 mg or Saroglitzazar magnesium 4mg.

6.4 Statistical Methods for Efficacy Analyses

The primary efficacy endpoint, change from baseline in ALP value at Week 16 will be analyzed separately for Saroglitzazar magnesium 2 mg and 4 mg using a two-sided paired t-test. The primary analysis will be performed using MITT population with LOCF as imputation method for missing values.

The analysis for the secondary efficacy endpoints, change from baseline in ALP at Week 4, Week 8, Week 12 and week 16, change from baseline in lipid profile (TG, TC, HDL, LDL, and VLDL), liver biochemistries (GGT, ALT, AST, bilirubin and albumin), serum total bile acids, 7 α -

Document Title:	Statistical Analysis Plan		
Version Number:	2.0	Date:	11 Nov 2019
Protocol Number:	SARO.16.004	Sponsor Name:	Zydus Discovery DMCC

hydroxy-4-cholesten-3-one (C4) and fibroblast growth factor 19 (FGF 19) and change from baseline in QoL (PBC40) total scores will be analyzed using ANCOVA (Analysis of covariance) model using baseline values and treatment as factors. The p-value for the treatment comparison, estimate of LSMEANS treatment difference (Saroglitazar magnesium (2 mg and 4 mg) – Placebo), and the 95% confidence interval of the LSMEANS difference will be generated from ANCOVA model. Observed and change from baseline values will be summarized descriptively at each visit for all secondary efficacy endpoints.

Frequency and percentage of subjects with ALP improvement of 15%, 20%, 30%, 40% and normalization (achieving abnormal to normal values) at Week 8 and Week 16 will be presented. Difference between the treatment groups will be presented using 95% exact confidence Interval for proportion.

For the PBC40 questionnaire responses, descriptive summaries will be provided for the total and also for each dimensional score.

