8.3.1.2 Modified intent-to-treat population

The modified intent-to-treat (MITT) population includes: all randomized subjects who received any study drug and have at least one post-randomized efficacy measurement.

All primary and secondary objectives will be analysed using MITT population with LOCF method. Last observation carried forward (LOCF) method will be used as an imputation method for the efficacy variables for MITT analysis.

 Zydus Discovery DMCC	CLINICAL TRIAL PROTOCOL Saroglitazar Magnesium – Phase II SARO.16.004	CONFIDENTIAL PAGE 57 OF 82
---	---	---

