6.8 Handling of Missing Data

Clarifications, wherever possible, will be obtained from the respective investigator for any missing data or for any illegible entry, unused or unauthenticated data. Subjects are required to have at least one post-treatment assessment to be included in the MITT population. Last Observation Carried Forward (LOCF) will be used for the imputation of missing values. Baseline values will not be carried forward for the imputation of missing values. Subjects discontinued from study will be excluded from the PP population.

Document Title:	Statistical Analysis Plan		
Version Number:	2.0	Date:	11 Nov 2019
Protocol Number:	SARO.16.004	Sponsor Name:	Zydus Discovery DMCC

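### LOCF assumes no change after a patient leaves, and the plan's one sensitivity analysis tests that only if dropout is unrelated to response

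*SAP*

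**What the plan says.** **Primary analysis (SAP 6.4).** The Week 16 ALP change "will be analyzed separately for Saroglitzazar magnesium 2 mg and 4 mg using a two-sided paired t-test", and "The primary analysis will be performed using MITT population with LOCF as imputation method for missing values".

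**Secondary continuous endpoints (SAP 6.4).** These "will be analyzed using ANCOVA (Analysis of covariance) model using baseline values and treatment as factors". No visit or subject term is listed. I read this as a separate fit at each week, although the SAP does not say so outright.

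**Timing (SAP 6.2).** ALP is scheduled repeatedly: "Change from baseline in ALP at Week 4, Week 8, and Week 12 and Week 16". Lipids, liver biochemistries and bile acids follow the same four weeks. C4, FGF19 and PBC-40 are Week 16 endpoints only.

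**Missing data.** SAP 6.8: "Last Observation Carried Forward (LOCF) will be used for the imputation of missing values", with the limit that "Baseline values will not be carried forward for the imputation of missing values". Protocol 8.3.1.2: "All primary and secondary objectives will be analysed using MITT population with LOCF method".

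**Checks on the result.** SAP 6.5 plans one sensitivity analysis, on the per-protocol population and directed at protocol deviations. SAP 6.8 removes discontinued subjects from that population. SAP 3.1 promises to discuss any MITT versus per-protocol inconsistency in key results.

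**Dropout.** Protocol 4.1 allows for 20% within 36 patients. Protocol 4.5 and 7.2 call for End of Treatment procedures when a patient leaves early.

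**The concern.** LOCF labels a value from an earlier point in treatment as the Week 16 value. If the ALP effect is still building when a patient leaves, the Week 16 mean change is pulled toward zero. If it is fading, the estimate is too large. This touches the primary within-arm change as well as the placebo comparisons.

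The per-protocol analysis leaves out exactly the patients whose values were imputed. If dropout is unrelated to response, a gap between the two populations would reveal the LOCF error. If poor responders tend to leave, the completers are themselves a selected group, and agreement or disagreement between the two analyses says little. The plan contains no other check on the assumption, although three intermediate visits are already collected and could inform it.

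**Working it through.** **Inputs from the documents:** 12 per arm; 20% dropout (0.20 × 12 = 2.4 patients per arm); visits at Weeks 4, 8, 12 and 16; LOCF from post-baseline values only. SAP section 4 reports no formal sample-size estimation, so there is no power figure to reproduce.

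**Assumptions (not in the documents):** the time course of the effect; leavers split evenly after Weeks 4, 8 and 12, so 0.20 / 3 = 0.0667 in each interval; dropout unrelated to response; no mean change on placebo.

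**Formula.** Attenuation as a share of the true Week 16 effect = sum over k of P(last value at k) × (1 − fraction of the effect reached at k). Under these assumptions it is the same for the within-arm change and for the difference from placebo.

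| Share of effect at Weeks 4/8/12/16 | Calculation | Attenuation |
|---|---|---|
| Flat, 100% throughout | 0.0667 × 0 | 0% |
| Early plateau, 85/95/100/100 | 0.0667 × (0.15 + 0.05 + 0) | 1.3% |
| 60/80/90/100 | 0.0667 × (0.4 + 0.2 + 0.1) | 4.7% |
| Linear, 25/50/75/100 | 0.0667 × (0.75 + 0.50 + 0.25) | 10% |
| Waning, 120/120/110/100 | 0.0667 × (−0.2 − 0.2 − 0.1) | −3.3% (over-estimate) |

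**With an exit value.** If the End of Treatment sample is taken on leaving, and patients leave midway between visits, the carried value is more recent:
- Linear: 0.0667 × (0.625 + 0.375 + 0.125) = 7.5%.
- 60/80/90/100: 0.0667 × (0.30 + 0.15 + 0.05) = 3.3%.

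**Simulation check** (3,000 replicates, 12 per arm, assumed true effect −1 SD, assumed correlation 0.7 between visits, last scheduled value carried forward):
- Random dropout of about 20%, linear growth: LOCF gives −0.90 SD both within arm and versus placebo. A repeated-measures likelihood estimate gives −1.00.
- Dropout depending on poor last response (about 23%), linear growth: LOCF gives −0.86 within arm and −0.91 versus placebo; repeated measures gives −1.00 for both.
- Same dropout, flat effect: LOCF gives −0.96 within arm but −1.03 versus placebo. The direction can differ between the primary and secondary analyses.

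**Unequal dropout (an assumption).** Take linear growth, 20% dropout on 2 mg and 30% on 4 mg, and the same true effect of −2 SD. Attenuation is 10% and 0.10 × 1.5 = 15%, so LOCF gives −2 × 0.90 = −1.80 and −2 × 0.85 = −1.70. Equal doses then appear 0.10 SD apart. A simulation with 10% dropout on placebo gave −1.79 and −1.69, against −1.99 and −2.00 for repeated measures. LOCF 95% interval coverage for 4 mg fell to about 90%.

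**Against sampling error.** The standard error of a placebo contrast is about √(2/12) = 0.408 residual SD.
- At a 1 SD effect, 10% attenuation is 0.10 / 0.408 = 0.245 standard errors. LOCF's relative root mean squared error is √(1 + 0.245²) = 1.03.
- At 2 SD it is 0.20 / 0.408 = 0.49 standard errors and √(1 + 0.49²) = 1.11.
- The repeated-measures standard error in simulation (assumed lag-1 correlation 0.84) ranged from about equal to 9% larger, so 1.00 to 1.09 on the same scale.

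**The case against.** **The effect need not be under-estimated.** A reader might infer that the plan will understate the ALP effect. The documents do not support that: they give no time course, and the result runs from a small over-estimate through zero to about 10%. This stands, and the point is therefore conditional.

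**Exit samples reduce the problem.** End of Treatment procedures at withdrawal make the carried value more recent. This stands. It lowers the figures to about 7.5% and 3.3% but does not remove the bias.

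**The per-protocol comparison is a check.** Under random dropout the completers' mean is unbiased, and SAP 3.1 commits to discussing discrepancies. This stands for random dropout only. Protocol 4.4.1 lists many laboratory triggers for stopping study drug, so random dropout should not be taken for granted.

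**Dose choice.** A reader might also infer that the phase III dose decision will be distorted. The link is indirect. SAP 2.5 assigns that decision to the interim analysis and states no imputation rule there, SAP 6.4 plans no 2 mg versus 4 mg contrast, and the documents give no dropout by arm.

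**Single-visit ANCOVA is not itself a fault.** With complete data it gives the same Week 16 contrast as the unstructured repeated-measures model with baseline-by-visit. This stands; the issue is LOCF, not the separate fits.

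**The gain is modest.** At a 1 SD effect, LOCF can match or beat the alternative on mean squared error. This stands. The alternative gains in bias, and at 2 SD with linear growth it gains in overall error as well.

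**Conclusion.** The point holds in conditional form. LOCF builds in an assumption of no change after leaving, for the primary within-arm ALP change and for the secondary ANCOVAs. The plan's only check works only if dropout is unrelated to response.

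At 20% dropout, with leavers spread evenly, attenuation is near 0% for an early plateau, about 3 to 5% for a 60/80/90/100% build-up and about 7.5 to 10% for linear growth. The lower ends apply if an exit value is taken midway between visits. A waning effect gives a small over-estimate. Unequal dropout, if it occurred, could also distort comparisons between doses. All time courses, effect sizes, correlations and arm-specific dropout rates here are assumptions.

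The size is modest in a 36-patient proof-of-concept trial. The change is still worth making: it uses data already collected and stops the primary result depending on an assumption the plan cannot reliably test.

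**What to change.** In SAP 6.4 and 6.8, for the endpoints measured at Weeks 4, 8, 12 and 16 (ALP, lipids, liver biochemistries, bile acids; not C4, FGF19 or PBC-40):

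- Fit one mixed model for repeated measures to observed values, without LOCF. Assign early End of Treatment values to a visit by a stated window.
- Include baseline, treatment, visit, treatment-by-visit and baseline-by-visit. Use an unstructured covariance with a pre-stated simpler fallback, and Kenward-Roger degrees of freedom.
- Report from this model the within-arm Week 16 ALP change for each dose (the primary quantity) and the contrasts versus placebo at each week.
- Keep the LOCF paired t-test and the LOCF ANCOVA as sensitivity analyses, listed in SAP 6.5.

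SAP section 1 allows revision before database lock, with reasons given in the study report. Protocol 8.3.1.2 also names LOCF, so the departure must be recorded against it.

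**Cost.** SAP wording and one extra model per endpoint; no new data or visits. The standard error is from about equal to 9% larger, and the unstructured covariance may not converge with 36 patients. The simulations used a likelihood point estimate and did not test the Kenward-Roger fit or its convergence. The model is valid only if dropout depends on values it contains; dropout driven by other laboratory results would not be covered by an ALP-only model.
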